Following the procedure, patients will rate their pain using a visual pain assessment scale at 1 hour postoperatively and at the time of discharge from the recovery room. Once the patient is at home, they will fill out a validated survey that has questions related to pain. This will be filled out once a day for a total of 7 days following the procedure. In addition, we will provide a medication utilization diary sheet for the patient to record daily use of prescribed narcotic and other as needed over the counter medications such as acetaminophen and ibuprofen. This will also be done daily for a total of 7 days. The patient will be surveyed at their one-week postoperative visit using the same assessment. All adverse drug reactions will be recorded from time of administration to initial follow-up. The following is the study schedule:

Study Schedule	Preop	Intraop	1hr post op	2 hr post op	1 week
Assessments					
Consent	x				
History and Physical	x				
Urine Culture					
Post URS medication record			x	x	
Pain Questionnaire	x		x	x	x
Adverse Events		x	x	x	x

4. Genetic Testing N/A

A. Describe

- i. the types of future research to be conducted using the materials, specifying if immortalization of cell lines, whole exome or genome sequencing, genome wide association studies, or animal studies are planned
- ii. the plan for the collection of material or the conditions under which material will be received
- iii. the types of information about the donor/individual contributors that will be entered into a database
- iv. the methods to uphold confidentiality

B. What are the conditions or procedures for sharing of materials and/or distributing for future research projects?

C. Is widespread sharing of materials planned?

D. When and under what conditions will materials be stripped of all identifiers?

E. Can donor-subjects withdraw their materials at any time, and/or withdraw the identifiers that connect them to their materials?

- i. How will requests to withdraw materials be handled (e.g., material no longer identified: that is, anonymized) or material destroyed)?

F. Describe the provisions for protection of participant privacy

G. Describe the methods for the security of storage and sharing of materials

5. **Subject Population:** Provide a detailed description of the types of human subjects who will be recruited into this study.

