For the current study, the following individuals, funding, and/or regulatory agencies will be notified (choose those that apply):

- All Co-Investigators listed on the protocol.
- Yale Cancer Center Data and Safety Monitoring Committee (DSMC)
- National Institutes of Health
- Food and Drug Administration (Physician-Sponsored IND # \_\_\_\_\_)
- Medical Research Foundation (Grant \_\_\_\_\_)
- Study Sponsor
- Other Data Safety Monitoring Board (DSMB) or Committee (DSMC)

The principal investigator [name] will conduct a review of all adverse events upon completion of every study subject. The principal investigator will evaluate the frequency and severity of the adverse events and determine if modifications to the protocol or consent form are required.

- d. For multi-site studies for which the Yale PI serves as the lead investigator: This is a single site study
  - i. How will adverse events and unanticipated problems involving risks to subjects or others be reported, reviewed and managed?
  - ii. What provisions are in place for management of interim results?
  - iii. What will the multi-site process be for protocol modifications?

**12. Statistical Considerations:** Describe the statistical analyses that support the study design.

*All data will be collected prospectively. Preoperative data will include patient demographics, number of previous URS, baseline medications including analgesics, urine culture, stone size and location, and pain questionnaire scores. Mean scores will be calculated and compared between groups stratified by follow-up time. The number of adverse events and hospital admissions related to pain will recorded and described as counts and percentages. The primary outcome that will be used to estimate effect size is mean post-operative pain.*

*Our study is set up as two independent groups with a continuous outcome (Pain measured on a 1-10 scale) and an enrollment ratio of 1. We anticipate mean post-operative pain in the non-intervention group to be 7 with a standard deviation of 2. We aim to detect a 10% difference in pain, in the intervention arm. With an alpha of 0.05 and a power of 80% we will need to enroll 63 patients in each arm.*

SECTION VI: RESEARCH INVOLVING DRUGS, BIOLOGICS, RADIOTRACERS, PLACEBOS AND DEVICES
--

*If this section (or one of its parts, A or B) is not applicable, state N/A and delete the rest of the section.*

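### The trial is sized for one comparison of mean post-operative pain, but the plan does not say which post-operative score, or which summary of them, that comparison uses.

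*Combined protocol and SAP*

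**What the plan says.** Section V, item 12 (Statistical Considerations) states: "The primary outcome that will be used to estimate effect size is mean post-operative pain". It treats this as one continuous outcome in two independent groups, on a 1-10 scale, with an expected control mean of 7 and SD of 2. The target and sample size follow: "We aim to detect a 10% difference in pain, in the intervention arm" and "With an alpha of 0.05 and a power of 80% we will need to enroll 63 patients in each arm". The one sentence on how pain is compared is "Mean scores will be calculated and compared between groups stratified by follow-up time".

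Section V, item 3 (Research Plan) sets out the collection of scores:

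- In recovery, patients rate pain "using a visual pain assessment scale at 1 hour postoperatively and at the time of discharge from the recovery room".
- At home, "they will fill out a validated survey that has questions related to pain", and "This will be filled out once a day for a total of 7 days following the procedure".
- At follow-up, "The patient will be surveyed at their one-week postoperative visit using the same assessment".

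The Study Schedule in the same item marks the pain questionnaire before surgery and at three post-operative times: 1 hour, 2 hours and 1 week. It has no column for the daily home surveys.

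The purpose (item 1), the hypothesis (item 2) and the aim (item 3) speak of post-operative pain or pain scores without a time.

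**The concern.** A single alpha of 0.05 and a single sample size presuppose a single test. Item 12 names one outcome but describes comparisons at each follow-up time, and does not say which of them, or what combination, is the primary result. The choice could then be made after the data are seen. If the most favourable time could be picked, the real false-positive risk would exceed the stated 5%. Item 3 has the surgical team un-blinded after the operation, which is a further reason to have the choice on record before scores are compared by arm.

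The gap also affects the sample size. The mean of 7 and SD of 2 carry no time, and pain an hour after surgery need not have the same mean or spread as pain a week later. Item 3 describes a visual scale in recovery and a survey at home, so choosing the time may also mean choosing the instrument.

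**Working it through.** **1. Count the scores.** Text of item 3: 1 hour (1) + recovery-room discharge (1) + daily home surveys (7) + one-week visit (1) = 10, or 9 if day 7 and the visit coincide. Schedule: 3. Recovery-room scores alone: 2. The second recovery-room score is tied to discharge in the text and to 2 hours in the schedule.

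**2. Reproduce the plan's figure.** Inputs from item 12: SD 2, alpha 0.05, power 80%, ratio 1. Sidedness is not stated; two-sided is assumed here. Using n per arm = 2 × (z for alpha + z for power)² × SD² / difference²:

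- 1.0 point: 2 × (1.960 + 0.842)² × 4 / 1.0² = 62.8, so 63. This matches the plan.
- 0.9 point (10% of the 9-point span of a 1-10 scale): 62.8 / 0.81 = 77.5, so 78.
- 0.7 point (10% of the mean of 7): 62.8 / 0.49 = 128.1, so 129.
- 0.9 point, one-sided: 2 × (1.645 + 0.842)² × 4 / 0.81 = 61.1, so 62. This is close to the plan's figure.

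Each calculation uses one score per patient; none allows for several times.

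**3. False-positive risk if any time could count.** For k two-sided tests at 0.05 with common correlation ρ between scores, the chance of at least one false positive is 1 − ∫ φ(z) [Φ((1.96 − √ρ z)/√(1−ρ)) − Φ((−1.96 − √ρ z)/√(1−ρ))]^k dz. At ρ = 0 this is 1 − 0.95^k. The documents give no correlations, so these are assumed.

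| Scores (k) | ρ = 0 | 0.3 | 0.5 | 0.7 | 0.9 |
|---|---|---|---|---|---|
| 2 (recovery room) | 9.8% | 9.5% | 9.1% | 8.4% | 7.0% |
| 3 (schedule) | 14.3% | 13.6% | 12.5% | 10.9% | 8.4% |
| 9 (text) | 37.0% | 32.6% | 26.9% | 20.2% | 12.4% |
| 10 (text) | 40.1% | 35.1% | 28.7% | 21.3% | 12.8% |

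If correlation instead decays with time between scores (first-order autoregressive, 0.3 to 0.9), the ranges are 9-14% for 3 scores and 17-39% for 9-10. With one pre-specified score the risk is 5%.

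**4. Does the choice change the sample size?** For a per-patient average of k scores, SD = 2 × √((1 + (k−1)ρ)/k), assuming SD 2 for each score. For a two-sided 1.0-point difference at 80% power and ρ of 0.5 to 0.9:

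- 3 scores: SD 1.63 to 1.93, needing 42 to 59 per arm.
- 10 scores: SD 1.48 to 1.91, needing 35 to 58 per arm.

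If every time were tested with a Bonferroni correction, 1.0 point at SD 2 would need 84 per arm for 3 scores, 105 for 9 and 107 for 10.

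**5. Related but separate: power of a single test.** Two-sample t-test, 63 per arm, SD 2, alpha 0.05:

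| Difference | Two-sided | One-sided |
|---|---|---|
| 1.0 point | 79.5% | 87.4% |
| 0.9 point | 70.7% | 80.7% |
| 0.7 point | 49.6% | 62.1% |

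**The case against.** The best defence is that item 12 contains two separate statements: one describes reporting by time, the other names a single primary outcome that may be meant as one summary. On that reading no multiple testing is prescribed. This stands in part: the text is ambiguous, and nothing in it says that each time is tested at 0.05 or that any one may count. A reader might infer that the trial runs a false-positive risk of 35% or more. The documents do not support that; the figures in step 3 are conditional. But no averaging rule is given either, and in a two-group design the mean may simply be the group mean at some time. The defence therefore does not identify the primary result.

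The 9-10 score range is also an upper case. The sample size assumes a 1-10 scale, and nothing says the home survey yields such a score. If only the two recovery-room ratings qualify, the range is 7-10%.

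A reader might also treat two different instruments as established. That is an inference from the wording: the schedule has one questionnaire row for all times, and the questionnaire that Section VII, item 11 says is attached was not available for review.

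Finally, a reader might conclude that 63 per arm gives 80% power only for 1.0 point. That does not follow, because sidedness is unstated, the hypothesis is directional, and a one-sided test of 0.9 point gives 80.7%. An average over times would also have a smaller SD. The meaning of the 10% is a separate sample-size question and adds no weight to this point.

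**Conclusion.** The concern holds in a limited form. The plan sizes the trial for one comparison, but the primary score cannot be identified from it, and its only comparison rule yields one comparison per follow-up time with no adjustment. This is more than missing detail, since it decides what the primary result is. That conclusion needs no assumption about correlation or sidedness.

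The size of the error risk does: about 7-10%, 8-14% or 12-35% for 2, 3 or 9-10 scores, given unadjusted two-sided tests, a common correlation of 0.3 to 0.9, and freedom to report any time as primary. The plan neither grants nor excludes that freedom. The mismatch between discharge and 2 hours is plain on the face of item 3.

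**What to change.** In Section V, item 12, before any scores are compared by arm:

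- Name one primary score, with its time and instrument, or one fully defined summary, and test it alone at 0.05. The 1-hour score is a reasonable example because it is already collected and appears in both text and schedule. The sponsor may prefer another time; Section VI, A.2 puts peak pain control at 75-150 minutes.
- Treat the other times as secondary with confidence intervals, or test them under a pre-specified error-controlling procedure such as a fixed sequence.
- Reconcile discharge with 2 hours for the second recovery-room score.
- Confirm that the mean of 7, the SD of 2 and the 1-10 scale apply to the chosen score, checking against the attached questionnaire.
- As a separate correction, state sidedness, give the 10% difference in points, and restate the power to match.

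**Cost.** Naming a score that is already collected is a wording change and does not itself alter enrolment. The sponsor gives up unadjusted claims of success at other times. The restated power may be less favourable: if the target is 0.7 point on a single score with SD 2, two-sided, it is about 50% at 63 per arm, and 80% would need about 129 per arm.

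### Comparing pain means separately at each time, with no rule for missing forms, is a weak analysis of the seven daily home scores; one repeated-measures model would handle incomplete diaries better

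*Combined protocol and SAP*

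**What the plan says.** Section V, item 3 (Research Plan) sets out three kinds of pain measurement after surgery. In hospital, "patients will rate their pain using a visual pain assessment scale at 1 hour postoperatively and at the time of discharge from the recovery room". At home there is a pain survey: "This will be filled out once a day for a total of 7 days following the procedure". In clinic, "The patient will be surveyed at their one-week postoperative visit using the same assessment". Section V, item 12 (Statistical Considerations) also lists pain questionnaire scores among the preoperative data.

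Item 12 gives one sentence on how scores are analysed: "Mean scores will be calculated and compared between groups stratified by follow-up time". It adds that "The primary outcome that will be used to estimate effect size is mean post-operative pain", without a time point. The sample size rests on three statements. For the control arm: "We anticipate mean post-operative pain in the non-intervention group to be 7 with a standard deviation of 2". For the size of the effect: "We aim to detect a 10% difference in pain, in the intervention arm". For the resulting number of patients: "With an alpha of 0.05 and a power of 80% we will need to enroll 63 patients in each arm".

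The plan names no test, repeated-measures model, analysis population or missing-data rule. The enrolment target in Section VII, item 1 is 126, exactly 2 × 63, so nothing is added for missing forms. The only safeguard for completeness is an eligibility item in Section V, item 7 on being ready to fill in the questionnaires.

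**The concern.** A form filled in at home on seven days will rarely come back complete. If arm means are compared one day at a time and nothing is said about missing forms, the natural default is to average whatever was returned that day. A patient who reported days 1 to 4 then contributes nothing to days 5 to 7, although the earlier scores say a good deal about the later ones.

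The trial hypothesises that the arms differ in pain. If a given level of pain makes patients stop reporting, whichever arm they are in, the control arm loses more of its high scorers. The remaining controls look more comfortable than the arm really is, and the difference shrinks. A likelihood-based repeated-measures model uses the earlier scores and corrects for this when missingness depends on pain already observed. At stake are the size and precision of the later home comparisons.

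**Working it through.** **Inputs from the plan.** Control mean 7, SD 2, 63 per arm, alpha 0.05 (taken as two-sided), power 80%, seven daily home scores. **Assumed, because the plan gives none:** loss rates, between-day correlation, the dropout mechanism, and the effect on each day.

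**1. The plan's figure.** n per arm = 2 × (1.960 + 0.842)² × SD² / δ². With δ = 1.0 (10% of a 10-point scale) this is 2 × 7.85 × 4 / 1 = 62.8, so 63; power is 80.1%. With δ = 0.7 (10% of 7) it is 62.8 / 0.49 = 128.1, so 129. The illustrations therefore use δ = 1.0, the reading that reproduces 63. The base of the 10% is a separate matter.

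**2. Direction, in a case that can be checked by hand.** Suppose everyone scoring above 9 stops, in either arm. The mean of those left is μ − 2·φ(a)/Φ(a), with a = (9 − μ)/2.
- Control, μ = 7, a = 1: 7 − 2 × 0.2420/0.8413 = 6.42; n = 63 × 0.8413 = 53.0.
- Drug, μ = 6, a = 1.5: 6 − 2 × 0.1295/0.9332 = 5.72; n = 63 × 0.9332 = 58.8.

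The difference falls from 1.00 to 0.70 and power to about 60%.

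**3. Other mechanisms.** If the worst 20% *within each arm* stop, the difference stays 1.00 and power is 91%. If low-pain patients stop first in both arms, it also shrinks (0.83–0.90). If drug patients leave at high pain and controls at low pain, it is overstated (1.69). The direction depends on the mechanism.

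**4. Simulated trials.** Settings: 63 per arm, SD 2, true difference 1.0 every day, dropout risk rising with the previous day's score by the same rule in both arms. Results are for day 7.

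| Loss, control / drug | Separate means: estimate, power | Repeated-measures model: estimate, power |
|---|---|---|
| 16% / 12% | 0.97, 72% | 1.00, 77% |
| 20% / 13% | 0.90–0.92, 66% | 0.99–1.00, 74–75% |
| 27% / 20%* | 0.94, 64% | 1.00, 71% |
| 28% / 20% | 0.92, 63% | 1.01, 73% |
| 36% / 25% | 0.83–0.90, 53–55% | 0.99–1.01, 71–74% |
| 38% / 28%* | 0.86, 53% | 0.98, 67% |
| 40% / 28% | 0.84, 53% | 1.00, 72% |

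*Covariance treated as known; in the other rows an unstructured covariance is estimated. Ranges cover between-day correlations of 0.5 and 0.7. With known covariance and 15% / 11% loss, the estimates are 0.99 and 1.02, a negligible gap.

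**5. How much is simply fewer patients?** Take 28% / 20% loss with no bias. Then n = 45.4 and 50.4, SE = 2 × √(1/45.4 + 1/50.4) = 0.409, and power = Φ(1/0.409 − 1.96) ≈ 69%. Of the fall from 80% to 63%, about 11 points come from lost patients and about 6 from the selective way they are lost. The model's 73% exceeds 69% because it also uses the earlier scores of patients who left.

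**6. Two limits.** If the true effect fades linearly from 1.0 to zero by day 7, the day-7 shift under separate means is only about 0.03–0.09 points. If dropout depends on the unseen same-day score, the model removes only part of the bias: it gives 0.98 at 20% / 13% loss and 0.87 at 50% / 33%.

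**The case against.** The strongest reply is that the plan does not commit to what is being criticised.

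- **Available cases.** A reader might infer that the plan specifies an analysis of returned forms only. It does not; that is the default when means are compared by time and nothing is said about missing data. This stands, and the point is worded accordingly.
- **Home scores.** The analysis sentence does not name them, and the schedule table in Section V, item 3 has no daily column. Still, the text of item 3 collects the survey daily, postoperative pain is an objective in Section V, item 1, and no other analysis is offered for these scores.
- **The primary result.** A reader might infer that the trial's main comparison is biased. The documents do not support that: the primary time point is not stated, and a score taken at 1 hour or at recovery-room discharge would be untouched by home dropout.
- **A constant effect to day 7.** This is doubtful for one intraoperative dose. Section VI, A.2 puts peak pain control at 75–150 minutes, and Section V, item 3 allows postoperative ketorolac. With a fading effect the bias is slight and there is no day-7 effect to lose power for. This stands and limits the size of the point.
- **The clinic score.** The one-week visit repeats the assessment and may fill some gaps near day 7. This also stands, and the fix uses it.
- **Known covariance flatters the model.** This does not stand: the gain persists when the unstructured covariance is estimated.

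**Conclusion.** The concern holds in a limited form. For repeated home scores, separate comparisons with no missing-data rule are an inferior choice, and a better one is available without new data. If the same level of observed pain triggers stopping in both arms and the effect stays at 1.0 point, the day-7 estimate loses about 0.06–0.09 points at roughly 28% / 20% loss, and power is about 63% rather than about 72%. At roughly 40% / 28% loss the estimate is 0.84–0.86, with power about 53% rather than 67–72%. At about 15% / 11% little is at stake.

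Two stronger conclusions do not follow. One is that the drug effect *will* be underestimated: even if patients in worse pain stop first, this requires a common pain threshold across arms, and other patterns leave the difference unchanged or inflate it. The other is that the size of loss shown is expected here: the documents give no loss rate, correlation or effect profile over time, so the figures are illustrations. The uncertain direction is itself a reason to fix the method in advance. The change is worth making, but it is not shown to threaten the primary result.

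**What to change.** In Section V, item 12, state that post-discharge pain scores will be analysed in one likelihood-based mixed model for repeated measures:

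- **Population:** all randomised patients, as allocated, with at least one post-discharge score.
- **Outcomes:** the seven daily home scores, plus the one-week visit score where it uses the same assessment.
- **Terms:** arm, day, arm-by-day and preoperative pain (already collected), with unstructured covariance.
- **Report:** the arm difference with 95% CI by day and averaged over days, and the number of forms returned per arm per day.
- **Sensitivity:** one analysis that worsens the missing scores, because the model corrects only for missingness that depends on observed pain.

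This should be written before outcome data are examined. It takes a few lines of text and standard software, with no new patients or measurements; the cost is slightly more analysis work. A patient who returns no diary and misses the visit contributes nothing to the model, so the form counts must be shown alongside it.

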**SECTION V: RESEARCH PLAN**

1. **Statement of Purpose:** State the scientific aim(s) of the study, or the hypotheses to be tested.

*The objective of this study is to evaluate the effect of a single intraoperative ketorolac injection on intra-operative narcotic use, postoperative pain and narcotic use, and hospital readmission rates in patients who undergo retrograde ureteroscopy for kidney and/or ureteral stone management.*

2. **Background:** Describe the background information that led to the plan for this project. Provide references to support the expectation of obtaining useful scientific data.

*The incidence and prevalence of urolithiasis in the United States has risen considerably over the past few decades.(1) Treatment for ureteral stones can include expectant therapy for asymptomatic and small stones,, shock wave lithotripsy (SWL) or ureteroscopy (URS) with lithotripsy for obstructing or symptomatic stones up to 15-20mm, and percutaneous nephrolithotomy for larger more complex stones.*

*Historically, SWL offered a non-invasive and effective intervention for the treatment of most symptomatic stones and was the preferred therapy. However, with advancement in ureteroscopic digital optics, miniaturization of scope caliber, improved flexibility and durability, and recognized better stone free rates, utilization of URS has steadily grown and is overtaking SWL as the preferred treatment modality for kidney stones. URS is accepted as the treatment of choice for lower ureteral stones and is associated with stone free rates of up to 100% by post-operative day 2.(2)*

*One limitation of URS is that post-operative pain due to intra-operative instrumentation and the common utilization of temporary ureteral stents can be challenging to manage. The complication rate for URS requiring postoperative hospital admission has been reported at up to 14%, with pain being the predominant complication.(4) This temporary post-operative pain and stent related colic is perhaps the greatest barrier, aside from surgeon skill, to the wider utilization of this URS over SWL, which has less efficacy but can be better tolerated. In addition to improving URS as a technology, we as physicians must improve the tolerance of URS for the patients.*

*Ketorolac is a non-steroidal anti-inflammatory drug (NSAID) available in oral or parenteral formulations. It is a highly effective analgesic with comparable potency to narcotics, non-*

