*habit forming, and without the gastro-intestinal (e.g. nausea, ileus, constipation) or neurologic side effects seen with narcotics. Ketorolac use is generally safe for short durations limited to less than 5 days. Contraindications including NSAID allergy, renal insufficiency, NSAID induced asthma, peptic ulcer disease, bleeding diathesis, pregnancy/breast feeding, or advanced age. The peri-operative use of ketorolac had been limited due to bleeding concerns. However, surgical studies have shown that its use in appropriately selected patients does not result in increased clinically significant bleeding but does improve pain control over placebo with reduced narcotic use. (6)*

*It has been previously shown that in-patients who undergo ureteral stent placement following SWL, the use of ketorolac as an intravesical agent significantly decreased discomfort 1 hour after treatment in comparison to patients who did not receive the treatment.(5) The safety of this was also confirmed as there were no postoperative side effects from the instillation.(5)*

*Currently, there is currently no consensus on standard of care regarding intraoperative analgesia for ureteroscopy. A ureteral stent is utilized in about 90% of patient. Patients are discharged with a prescription for oral narcotics and stents are usually removed on post-operative day 5-7.*

*To the best of our knowledge there have not been any prospective studies that have evaluated the use of intraoperative ketorolac in patients who undergo URS, regardless of stent placement, to minimize postoperative pain. We hypothesize that patients who receive intraoperative ketorolac during URS will have improved outcomes with regards to postoperative pain assessment as well as decreased pain related hospital admissions in comparison to patients with no treatment.*

- 3. Research Plan:** Summarize the study design and research procedures using non-technical language that can be readily understood by someone outside the discipline. **Be sure to distinguish between standard of care vs. research procedures when applicable, and include any flowcharts of visits specifying their individual times and lengths.** Describe the setting in which the research will take place.

*This is an investigator-initiated, single-center, prospective randomized clinical trial evaluating the efficacy of intraoperative Ketorolac on post-operative pain in patients undergoing ureteroscopy at Yale-New Haven Hospital.*

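### The protocol hypothesizes fewer pain-related admissions, but the statistical section plans only counts and percentages for them, with no between-arm difference or interval

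*Combined protocol and SAP*

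**What the plan says.** The Statement of Purpose (Section V, item 1) sets out to evaluate the effect of ketorolac on several outcomes, among them "postoperative pain and narcotic use, and hospital readmission rates in patients who undergo retrograde ureteroscopy". The Background (Section V, item 2) ends with a directional hypothesis: better postoperative pain assessment, "as well as decreased pain related hospital admissions in comparison to patients with no treatment". The same section gives the only admission rate in the documents: "The complication rate for URS requiring postoperative hospital admission has been reported at up to 14%, with pain being the predominant complication".

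The Statistical Considerations (Section V, item 12) treat the two outcomes differently. Mean pain scores are to be compared between the arms. For admissions the plan is: "The number of adverse events and hospital admissions related to pain will recorded and described as counts and percentages". Item 12 then says "The primary outcome that will be used to estimate effect size is mean post-operative pain", and the sample size follows from that outcome only: "We anticipate mean post-operative pain in the non-intervention group to be 7 with a standard deviation of 2", and "With an alpha of 0.05 and a power of 80% we will need to enroll 63 patients in each arm". No test, interval, expected rate or power is stated for admissions.

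Section IX lists a lower risk of readmission as a possible benefit. It adds that a negative result would discourage use of the drug.

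**The concern.** A hypothesis of a decrease relative to the control arm is a statement about a difference between arms. The planned output is one percentage per arm, with no estimate of that difference and no measure of its uncertainty. So the plan states a hypothesis and provides no analysis that speaks to it.

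What is at stake is how the result will be read. With few events per arm, a gap of several percentage points can arise by chance, and a real reduction can fail to show. If the final report sets two percentages side by side, a reader who knows the hypothesis may take a gap as support and similar figures as refutation. Section IX makes the second reading a practical matter, because it already says what would follow from finding no benefit.

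**Working it through.** **Inputs from the documents.** 63 per arm, 1:1 allocation, alpha 0.05, 80% power, and for pain a control mean of 7 with SD 2 (Section V, item 12). Admission rate of up to 14% (Section V, item 2), an upper figure for all complications requiring admission, of which pain is the commonest.

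**Assumptions.** Two-sided alpha, since the plan does not state sidedness. 14% as a ceiling for the control-arm rate of pain-related admission. A halving in the treated arm. A lower scenario of 10% versus 5%. The documents give neither a pain-only rate nor an expected reduction.

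**Step 1: the plan's own figure.** n per arm = 2(1.960 + 0.842)² × SD² / Δ². With SD = 2 and Δ = 1 point this is 2 × 7.849 × 4 / 1 = 62.8, so 63. The stated number reproduces for a 1-point difference in mean pain, and admissions play no part in it. (Taking the 10% difference relative to the mean of 7, or 0.7 points, would give a different number. That is a separate matter and does not affect this point.)

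**Step 2: expected admissions.** At 14% and 7%: 63 × 0.14 = 8.8 and 63 × 0.07 = 4.4 patients.

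**Step 3: precision and power for 14% versus 7%.**
- Standard error of the difference: √(0.14 × 0.86/63 + 0.07 × 0.93/63) = 0.0543. The 95% half-width is 1.96 × 0.0543 = 10.6 percentage points, against a true difference of 7.
- Normal approximation with pooled variance: mean rate 0.105, null standard error √(2 × 0.105 × 0.895/63) = 0.0546. Power = Φ[(0.07 − 1.96 × 0.0546)/0.0543] = Φ(−0.68) = 25%.
- Exact enumeration over two binomials with n = 63 each: chi-square 24.8%, Fisher mid-p 23.1%, Fisher exact 16.2%.
- One-sided at 0.05: 36% (normal approximation) or 27% (Fisher).
- For scale only, n per arm for 80% power = [1.960√(2 × 0.105 × 0.895) + 0.842√(0.14 × 0.86 + 0.07 × 0.93)]² / 0.07² ≈ 300.

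**Step 4: other assumed rates (exact enumeration, two-sided).**

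| Control vs treated | Fisher | Chi-square |
|---|---|---|
| 14% vs 7% | 16% | 25% |
| 10% vs 5% | 10% | 18% |
| 14% vs 3.5% | 43% | 58% |

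**Step 5: what bare percentages could show by chance.**
- If both arms truly ran at 14%, a gap of at least 5 patients (5/63 = 7.9 points) in either direction would occur about 25% of the time, and in ketorolac's favour about 12%.
- If the rate were truly halved from 14% to 7%, the treated arm would still have as many or more admissions about 12% of the time.

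**Step 6: what an interval would add.** Suppose 9/63 (14.3%) versus 4/63 (6.3%) is observed. The Wilson 95% limits are 7.7% to 25.0% and 2.5% to 15.2%. Newcombe's interval for the difference of 7.9 points is:
- lower: 7.9 − √[(14.3 − 7.7)² + (15.2 − 6.3)²] = −3.1 points
- upper: 7.9 + √[(25.0 − 14.3)² + (6.3 − 2.5)²] = 19.3 points

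Fisher's p is 0.24. The percentages alone suggest that admissions more than halved. The interval shows that no difference, and a small difference the other way, remain compatible with the data.

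**The case against.** The strongest reply is that item 12 already treats admissions as descriptive. It names one primary outcome, sizes the trial on it, and promises no test of admissions. Low power for an uncommon binary outcome that is not primary is not a design error. The Statement of Purpose is neutral (evaluate the effect), the Research Plan gives pain scores as the reason for the study, and Section IX says only that patients may benefit. Anyone given counts and arm sizes can also work out the interval.

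Much of this stands. A reader might infer from the power figures that the trial is too small. The documents do not support that: they claim no power for admissions, and the primary sample size does not depend on them. A reader might also infer that admissions carry equal rank with pain because the hypothesis names two things. Nothing gives them that rank. And 14% should not be read as the protocol's pain-admission rate. It is an upper figure for all complications requiring admission, and the halving is an assumption of this review. A lower pain-only rate would reduce power further, so that correction does not weaken the point.

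What does not fall away is the mismatch. No section labels admissions exploratory, and the Background predicts a decrease. That a reader could compute the interval is no reason for the report to leave it out.

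**Conclusion.** The point holds as a mismatch between a stated hypothesis and its planned analysis. Section V hypothesizes fewer pain-related admissions, and item 12 provides no between-arm estimate or interval for them. If 14% is a ceiling for the control rate and ketorolac halves it, power at 63 per arm is about 16% to 25%, depending on the test. It is about 10% to 18% at an assumed 10% versus 5%. These figures rest on two-sided alpha, full data on all 126 patients and the assumed rates. They show why percentages alone could mislead and are not evidence of an error in the sample size.

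A reader might go further and infer that the trial should be barred from any statement about admissions, for or against. That is too strong. A large effect could show: at an assumed 14% versus 3.5%, power is 43% to 58%. The interval should carry the interpretation, whatever it turns out to be.

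The point is worth correcting and modest in weight. The main analysis of pain is unaffected.

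**What to change.** In Section V, item 12, replace the descriptive-only plan for admissions with this: report, per arm, the number and percentage of patients with at least one pain-related admission, together with the between-arm risk difference and its 95% confidence interval (Newcombe, for example). Add that admissions are a secondary or exploratory outcome, that the trial is not powered for them, and that any conclusion about them will rest on the interval.

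In the hypothesis sentence at the end of the Background (Section V, item 2), give admissions the same secondary or exploratory label so that the two sections agree.

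The cost is a few words and one more table line, with no added patients and no change to trial procedures. The downside is a softer claim about admissions.
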